**A.4.A.5. Is there an Investigational New Drug application (IND) for this study?**

No

Please check below:

This study does not involve drugs, biologics or other substances.

**A.4.A.6. Will this study involve investigational devices, instruments, machines or software?**

No

**A.4.A.7. Does your study involve any of the following? (check all that apply)**

Embryonic stem cells

Fetal tissue

Genetic testing (see [GINA](#) and [GWAS](#))

Clinical laboratory tests

If McLendon Labs will do the testing, you must complete the appropriate form found at [UNC Health Care](#) and submit to them for review.

Testing for communicable diseases that have mandated reporting requirements ([link to state guidance](#))

Point of Care Testing (POCT), which is CLIA-approved testing done at the "bedside" or site of care by hospital or clinic personnel (not by subject). Examples include urine pregnancy testing, glucose monitoring, etc.

If McLendon Labs will do the testing, you must complete the POCT form found at [UNC Health Care](#) and submit to them for review.

Diagnostic or therapeutic ionizing radiation, or radioactive isotopes, which subjects would not receive otherwise if not participating in this research study. Do not check if all radiation is administered as standard of care. ([Human Use of Radiation in Research](#))

Gadolinium administered as a contrast agent

Recombinant DNA or gene transfer to human subjects

#### A.4.A.8. Will your study involve storage of specimens for future unspecified research?

No

### A.5. Benefits to subjects and/or society

#### A.5.1. Describe how this study will contribute to generalizable knowledge that will benefit society.

NPWT has been increasing in utility in both orthopaedics and general surgery. Originally designed for open wounds the use of NPWT on clean surgical incisions for wound healing and the prevention of infection is relatively new. No study has been done evaluating multiple aspects of wound healing on clean incisions. This study will further evaluate the use of NPWT on closed incisions and their role in improving wound healing. We anticipate that the proposed study will provide further evidence to support NPWT on clean, closed incisions in primary total hip arthroplasty.

The prevention of infection is extremely important in total joint surgery. Periprosthetic joint infections are a devastating complication due to their difficulty in treating, burden on the system, and patient morbidity and occurs in approximately 0.5% to 3% of primary total joint arthroplasties. Revision total knee has both a detrimental physical and economic burden. Patients require treatment with intravenous antibiotics, multiple surgeries, and prolonged hospital courses. The clinical outcome of revision surgery for infection is also worse compared to other reasons for revision. Periprosthetic infections also place a significant burden on hospitals. Increased blood loss, complications, and operative time lead to higher total hospital costs, longer hospital stays and increased outpatient visits. Revision arthroplasty compared to aseptic revision can cost more than \$60,000 more. The cost of revision total joint arthroplasty is expected to be 1.6 billion in 2020. Any method that can help reduce the risk of infection stands to benefit both the patient and society.

#### A.5.2. Does this study have the potential for direct benefit to individual subjects in this study?

Yes

*Consider the nature, magnitude, and likelihood of any direct benefit to subjects. If there is no direct benefit to the individual subject, say so here and in the consent form, if there is a consent form. Do not cite monetary payment or other compensation as a benefit.*

Explain

The negative pressure device may decrease the risk of infection which is a devastating complication of total hip arthroplasty. Although it may decrease risk the incidence of infection is low(0.5 to 3%)

of the population so it is unlikely that any one individual has a change in outcome. However, the decrease in risk can be seen as a substantial benefit over the entire total hip arthroplasty population.

A.5.3. Are there plans to communicate the results of the research back to the subjects?

No

## A.6. Risks and measures to minimize risks

*For each of the following categories of risk you will be asked to describe any items checked and what will be done to minimize the risks.*

A.6.1. Psychological

- Emotional distress
- Embarrassment
- Consequences of breach of confidentiality (Check and describe only once on this page)
- Other

A.6.2. Describe any items checked above and what will be done to minimize these risks

A.6.3. Social

- Loss of reputation or standing within the community
- Harms to a larger group or community beyond the subjects of the study (e.g., stigmatization)
- Consequences of breach of confidentiality (Check and describe only once on this page)
- Other

A.6.4. Describe any items checked above and what will be done to minimize these risks

. Research data will be identified only by study identification numbers (IDs). These study IDs will be used to maintain relationships in the data between various tables. All consent forms and any paper data collection instruments will be stored in a locked cabinet in a secure location. The list identifying subjects with their contact information will be kept separate from the scientific study data. Data will be managed with REDCap software to help with data security and remain on password protected hardware.

A.6.5. Economic

- Loss of income
- Loss of employment or insurability
- Loss of professional standing or reputation
- Loss of standing within the community

Consequences of breach of confidentiality (Check and describe only once on this page)

Other

A.6.6. Describe any items checked above and what will be done to minimize these risks.

No Answer Provided

A.6.7. Legal

Disclosure of illegal activity

Disclosure of negligence

Consequences of breach of confidentiality (Check and describe only once on this page)

Other

A.6.8. Describe any items checked above and what will be done to minimize these risks

No Answer Provided

A.6.9. Physical

Medication side effects

Pain

Discomfort

Injury

To a nursing child or a fetus (either through mother or father)

A.6.10. Describe any items checked above, including the category of likelihood and what will be done to minimize these risks. Where possible, describe the likelihood of the risks occurring, using the following terms:

- Very Common (approximate incidence > 50%)
- Common (approximate incidence > 25%)
- Likely (approximate incidence of 10-25%)
- Infrequent (approximate incidence of 1-10%)
- Rare (approximate incidence < 1%)

Potential Risks. The potential risks to the research subjects include

INFREQUENT/RARE -- surgical site infection(known risk factor that we are evaluating)-Patients will undergo surgery with sterile technique. They will be monitored throughout the postoperative course for signs of infection.

RARE -- unanticipated adverse events, allergic reaction- -- Screening to exclude patients with known contraindications to the study dressing including silver and adhesive and obtaining care early for any adverse events or allergic reactions, departing from protocol to provide care as necessary to address side effects and adverse events that are not expected

INFREQUENT -- skin sensitivity to the dressing, Taking care to decrease the pain with dressing removal including the use of rubbing alcohol as needed

A.6.11. Unless already addressed above, describe procedures for referring subjects who are found, during the course of this study, to be in need of medical follow-up or psychological counseling

Any study device leading to serious allergies or adverse side effects will be discontinued. Research related injuries will be treated at UNC Hospitals if desired by the patient. The subject or their insurance company will be billed for this treatment, in the usual manner.

A.6.12. Are there plans to withdraw or follow subjects (or partners of subjects) who become pregnant while enrolled in this study?

No

## A.7. Data and safety monitoring

A.7.1. When appropriate, describe the plan for monitoring the data to ensure the safety of participants.

These plans could range from the investigator monitoring subject data for any safety concerns to a sponsor-based data and safety monitoring board or committee (DSMB, DSMC, DMC), depending on the study. For studies that do not raise obvious safety concerns, you may still describe your plans for monitoring the study as it progresses.

The investigator and the attending's nurse will be monitoring the patients continuously as the study progresses. Patients will be in the hospital for 2-3 days following surgery and will return to clinic around post op day 7 and 14. During that time they will be maintained on a monitoring list to identify any readmissions and to ensure appropriate followup. They will have a number for any issues and these will be provided to the research team to ensure appropriate care.

A.7.2. If not already addressed above, describe the plans for aggregate review of unanticipated problems (including but not limited to adverse events) across all sites, in order to monitor subject safety.

Any adverse event/unanticipated problem will result in disclosure to the IRB and proper response by the PI and investigator team.

A.7.3. What are the criteria that will be used to withdraw an INDIVIDUAL SUBJECT from this study or halt the research intervention (e.g., abnormal lab tests, allergic reactions, failure or inability to comply with study procedures, etc.)?

Patients that sustain allergic reactions, complications necessitating further treatment, or other unanticipated adverse event will be withdrawn from the study and proper care initiated.

A.7.4. Are there criteria that will be used to stop the ENTIRE STUDY prematurely (e.g., safety, efficacy, unexpected adverse events, inability to recruit sufficient number of subjects, etc.)?

Yes

Please explain

If a significant percentage of patients in the treatment group have unanticipated adverse events or any concern for their short/long term safety the project will be halted immediately. If it does not appear that we will be able to establish our numbers in 1 year, the project will be halted.

We anticipate being able to sign up 2 patients a week. If we are averaging less than 1 patient a week for a month we will stop the study. As this will likely be difficult to recover from.

Any noticeable increase in significant postoperative complications would lead us to stop the study early however specific numbers will likely depend on the type of adverse event. For instance if 3 hips require surgical irrigations that would be a significant increase. However 3 surgical wounds that have significant erythema would not be a significant increase. We will have to remain aware of the status of these patients and be willing to be cautious if any noticeable increase in adverse events beyond what is expected occurs.

Adverse events will be graded on a 1-5 grading scale in line with the NIH adverse outcomes grading. Most relevant to our study will be adverse outcomes related to allergic reactions although any adverse outcome will be applied.

Grade 1 Mild AE, no intervention required

Grade 2 Moderate AE, local or noninvasive intervention required

Grade 3 Severe AE, invasive or hospitalization may be required

Grade 4 Life-threatening or disabling AE, urgent intervention may be required

Grade 5 Death due to AE

Grade 1 –Transient allergic reaction, such as itching, mild pain

2 – Localized rash or erythema, skin damage

3 – Full body urticarial, edema, excessive bleeding

4 – Bronchospasm, hypotension

5 – Death due to adverse event

If a significant number of adverse events occur we will discontinue the study immediately. Given the very low likelihood of adverse events related to this study we will have a low threshold to discontinue the study. Therefore, if 3 cases (This would then be 3% of the final number of participants) of serious adverse events (greater than grade 3) this will result in discontinuation of the study. This threshold was set due to the reported rate of allergic reaction and adverse events of this product being less than 1%. If 3% of patients are experiencing severe effects, than this would be over 3 times the expected percentage. This may be due to chance because of our low number of subjects. But given the severity and the possibility that this increase may be due to our specific institutions care routine, specific device, or other problems associated with our care it is reasonable to set this low threshold.

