**Table 1b. Measurements Recorded: Treatment and Response Data**

Measurement	1 Week Post op	2 Weeks Post op
Serous Exudate	X	X
Erythema	X	X
Purulent Exudate	X	X

Separation of Deep Tissue	X	X
Antibiotic Treatment	X	X
Local Debridement	X	X
Operative Debridement	X	X
Positive Bacterial Culture	X	X
Hospitalization >14 days	X	X
Adverse Events	X	X

A.4.3. If subjects are assigned or randomized to study "arms" or groups, describe how they are assigned.

- *Describe the methods of computing the randomization schedule (if any) and maintaining blinding (if any).*
- *Who will perform these computations?*
- *How will you verify each subject's eligibility prior to randomization?*

Treatment regimen will be assigned to research subjects by a randomization procedure performed through the REDCap software. An independent member of the TraCS team and software manager ([name]) will assist in developing the randomization. Prior to surgery the research team will be informed of the selected treatment group and provide the dressing to the surgeon intraoperatively. Subsequently, the assigned treatment may be adaptively modified in some ways to protect the well-being of the subject. Such modifications may create a departure from protocol.

Randomization procedure. The randomization procedure will assign the research subjects (i.e., the experimental units) to the two treatment regimens in a 1:1 ratio. De

Blinding. This will be an unblinded, open-label study. Both patients and their respective care teams will be aware of the treatment regimen to which each patient has been randomized at the time of enrollment, at the time of informed consent and throughout treatment.

Protocol Departures. Although early termination of the subject's dressing is not anticipated, it is possible that some research subjects will require modifications of their dressing or care that constitute departure from the assigned treatment regimen. A case by case decision will be made to either continue the protocol or to drop the patient from the study and make needed changes. Protocol departures will be carefully documented. Subjects whose medical care departs from the protocol will continue to be evaluated per protocol and the resulting data will be recorded in the database for use in intent-to-treat (ITT) statistical analyses.

A.4.4. Describe any follow up procedures.

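### A.7.3 withdraws patients for events that overlap with the outcomes, A.4.3 promises continued evaluation, and A.8.1 does not say that the primary test is by assigned arm

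*Combined protocol and SAP*

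**What the plan says.** **Withdrawal rule, A.7.3.** The form asks for criteria to "withdraw an INDIVIDUAL SUBJECT from this study or halt the research intervention", so it covers two different actions. The answer names only the first: "Patients that sustain allergic reactions, complications necessitating further treatment, or other unanticipated adverse event will be withdrawn from the study and proper care initiated".

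**Departure rule, A.4.3 (Protocol Departures).** The paragraph first says: "A case by case decision will be made to either continue the protocol or to drop the patient from the study". It then says: "Subjects whose medical care departs from the protocol will continue to be evaluated per protocol and the resulting data will be recorded in the database". The stated purpose is intention-to-treat analysis, and this is the only mention of intention to treat in the document.

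**Risk section.** Among the measures against rare events, A.6.10 lists "departing from protocol to provide care as necessary to address side effects and adverse events that are not expected". A.6.11 adds: "Any study device leading to serious allergies or adverse side effects will be discontinued".

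**Analysis and sample size.** A.8.1 gives the null hypothesis for the week-1 ASEPSIS score and a two-group t-test. It names no analysis set and does not say how missing scores are handled; sensitivity analyses appear only in connection with the exploratory modelling. A.8.4 plans for 80 patients to finish out of as many as 90 recruited, with about 10 expected to have incomplete data.

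**The concern.** A patient with an unexpected adverse event or a treated wound complication meets the A.7.3 withdrawal rule. The same patient's care is a departure under A.6.10, and A.4.3 then says both that the patient may be dropped and that evaluation goes on. Nothing states which rule governs data collection.

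This matters because the triggers are not neutral. They are the kind of event that the score and the secondary aims are meant to capture. If patients leave data collection because their wound did badly, the remaining patients are no longer the randomised groups, and the covariate balance that A.8.1 draws from randomisation is no longer assured. The trial is open-label, so a case-by-case decision to drop a patient is made with the arm known, and only one arm wears the device. Loss could therefore differ by arm, though the documents do not show that it will.

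The main thing at stake is whether the primary comparison is truly by assigned arm. Aim 2 events are already exploratory under A.8.4.

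**Working it through.** **1. Overlap of triggers and outcomes.** The scoring table in A.1.1 gives 10 points for antibiotics, 5 for local debridement, 10 for debridement in the operating room and 10 for isolated bacteria. Table 1b records these at weeks 1 and 2. Aim 2 counts aspirations, emergency visits and returns to theatre, and Aim 3 counts adverse events (A.1.2). A complication that needs more treatment is thus both an A.7.3 trigger and, in many cases, an outcome.

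**2. What can go missing.** The week-1 score is exposed only to withdrawals before the day-7 visit. The day-2 dressing change (A.4.2) is one scheduled point at which a reaction could be seen before then. Later withdrawals expose the week-2 score. The triggering event itself is probably recorded.

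**3. The plan's own figures.** Inputs from A.8.4 are 40 per arm, 0.63 SD and 80% power. Two-sided alpha of 0.05 is assumed, because the plan does not state it.
- Normal approximation: Φ(0.63 × √(40/2) − 1.96) = Φ(0.857) = 80.4%. The noncentral t gives 79.5%. The stated 80% reproduces.
- Recruitment: 80 / (1 − 10/90) = 90, as stated.
- Losing two more patients per arm (38 and 38) leaves power of about 77%, so loss of numbers is not the problem.

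**4. How many patients.** The documents give no rate of treated complications. The infection range of 0.5% to 3% (A.1.1) can serve only as a proxy.
- 90 × 0.005 = 0.45 and 90 × 0.03 = 2.7 patients.
- Events that A.6.10 rates as rare (below 1%) add fewer than 90 × 0.01 = 0.9.

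The infection range has no time window, so these are not counts of withdrawals before day 7.

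**5. Effect on the estimate.** Losing one patient who carries 10 extra points moves an arm mean by about 10/40 = 0.25 points, or 10/45 = 0.22.

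For an illustration, assume complications in 3% of controls and 0.5% of NPWT patients, 10 points each, all present by week 1, and no other difference. The excess is 10 × 0.03 = 0.30 points in controls and 10 × 0.005 = 0.05 in NPWT. The difference below is control minus NPWT, so a positive value favours NPWT.

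| Complicated patients lost | Estimated difference |
|---|---|
| None | 0.30 − 0.05 = 0.25 |
| All, both arms | 0 − 0 = 0 |
| Controls only | 0 − 0.05 = −0.05 |
| NPWT only | 0.30 − 0 = 0.30 |

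The documents give no basis for choosing a row.

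**The case against.** The strongest reply is that the plan already contains the answer. A.4.3 promises continued evaluation for intention to treat, A.6.10 places care for unexpected events under departures, and the A.7.3 question also covers halting the intervention. The author may have meant only that the dressing is stopped. That reading is fair. It does not close the gap, because the A.7.3 answer speaks only of leaving the study, A.4.3 itself permits dropping a patient, and A.8.1 does not carry the intention-to-treat principle to the primary test.

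A second reply is that later events are unlikely to vanish. A.4.2 monitors patients to the 6-week visit, A.4.4 calls follow-up normal care, A.7.1 tracks readmissions and A.8.5 draws on medical records. This largely stands: loss of Aim 2 and Aim 3 events is uncertain, and the wound scores are the more exposed data.

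A third reply is that the shifts in the illustration are below the 1 to 2 points that A.8.4 puts down to observer differences. That also stands, and it limits the weight of the point.

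Some stronger readings are tempting but not supported:
- A reader might infer from the 80 finishing patients in A.8.4 that a completers analysis is planned. That count fits an intention-to-treat analysis equally well.
- A reader might see A.6.11 as a further conflict. It only discontinues a device and does not end data collection.
- A reader might count "skin sensitivity to the dressing" as a trigger. The form's band of 1% to 10% for that risk would give 0.9 to 9 of 90. A.6.10 lists it apart from allergic reaction, although the grading examples in A.7.4 include itching and local rash. Whether it triggers withdrawal is not stated.

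**Conclusion.** The conflict in the text is clear: A.7.3 and A.4.3 give different rules for overlapping events, A.4.3 is not consistent within itself, and A.8.1 leaves the analysis population open. It should be fixed, because following A.7.3 as written would make scores missing for reasons tied to outcome.

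The consequence is conditional. It depends on A.7.3 being applied literally and, for the primary endpoint, on withdrawal before day 7. The size is unknown and probably small. The range of −0.05 to 0.30 around a true 0.25 points rests wholly on the assumed rates, points and timing. A reader might infer that the bias favours the device. The documents do not support that: in the illustration, losing every complicated patient moves the estimate towards zero, and the direction otherwise depends on which arm loses more.

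**What to change.** Leave every clinical decision as it is and change only what happens to the data.

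- **A.4.3 and A.7.3.** Reconcile the two so that stopping or changing the study dressing does not end data collection. State that ASEPSIS scores at the Table 1b visits (weeks 1 and 2), and complications and adverse events to the 6-week visit, continue to be recorded unless the patient withdraws consent. Tying scores to Table 1b avoids relying on the week-6 score, which Aim 1 mentions but Table 1b does not schedule. A.6.11 needs no edit.
- **A.8.1.** State that the primary comparison is by assigned arm and includes every randomised patient with a week-1 score, whatever dressing was received. Specify a sensitivity analysis for missing week-1 scores, for example one that fills them with a range of values, varied by arm, and shows where the conclusion would change.
- **Reporting.** Give withdrawals and missing scores by arm, day and reason.

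The cost is a few sentences, scoring a few more patients at visits that are already standard care, and one extra sensitivity analysis.

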### A.4. Study design, methods and procedures

*Your response to the next question will help determine what further questions you will be asked in the following sections.*

A.4.1. Will you be using any **methods or procedures commonly used in biomedical or clinical research** (this would include but not be limited to drawing blood, performing lab tests or biological monitoring, conducting physical exams, administering drugs, or conducting a clinical trial)?

Yes

A.4.2. Describe the study design. List and describe study procedures, including a sequential description of what subjects will be asked to do, when relevant.

Patients will undergo primary total hip arthroplasty with identical preoperative and intraoperative care. The patients will then be divided into two groups depending on their randomization. All postoperative care will remain the same other than the choice of dressing placed postoperatively. They will remain in the hospital for 2-3 days(standard of care). On Post op day two they will receive a dressing change regardless of their regimen(standard of care). Patients will be discharged home or to a skilled nursing facility with instructions regarding wound care in both regimens. They will receive assistance through home health or through their nursing facility in case of dressing issues although there will be no intended dressing change or other alteration of the dressing until their next followup. Instructions for the study will be included in the discharge instructions and

include a phone number for questions, these instructions are provided on another attachment. The patients will return to clinic on Post op day seven. They will have their wound evaluated and the dressing changed with their wound evaluated for ASEPSIS (the details of the scoring system and references are provided in the background). They will return on post op day 14 and again have their wound evaluated. Their staples will also be removed. They will be monitored until their 6 week visit for any complications.

Standard Regimen.

Post Op Dressing	Staples over surgical incision, Adaptic® dressing, Abdominal Dressing pad, Tape
POD2	All dressings removed, staples remain in place, Island dressing placed
1 Week Post Op	Island dressing removed and new sterile island dressing placed *Wound evaluated
2 Weeks Post Op	Island dressing removed and staples removed, no dressing placed *Wound evaluated

Experimental Regimen.

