Followup is standardized and in keeping with normal postoperative care. Evaluation of the wound will occur during followup, however no additional procedures will be required.

A.4.5. Once this study has been approved by the IRB, for how many months or years will this study be active (you are collecting data or have access to identifiers)?

Start:Following IRB approval

Stop: 1 year from start date or earlier depending on number enrolled

A.4.6. Will this study use any of the following methods?

- Audiotaping
- Videotaping or filming
- Behavioral observation - (e.g., Participant, naturalistic, experimental, and other observational methods typically used in social science research)
- Pencil and paper questionnaires or surveys
- Electronic questionnaires or surveys
- Telephone questionnaires or surveys
- Interview questionnaires or surveys
- Other questionnaires or surveys
- Focus groups
- Diaries or journals
- Photovoice
- Still photography

A.4.7. If there are procedures or methods that require specialized training, describe who (role/qualifications) will be involved and how they will be trained.

Physical examination will be performed by 2 orthopaedic clinic members that do not require additional training. Dressing care will be provided by nursing staff, home health, and skilled nursing facilities with proper training. The nurses involved in patient care are not required to do any additional tasks. They can monitor the status of the dressing and will inform the clinic team if a dressing is malfunctioning. They will not be asked to do dressing changes. The device is designed to not require any daily maintenance.

A.4.8. Are there cultural issues, concerns or implications for the methods to be used with this study population?

No

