**A.8.4. Provide a compelling justification for the proposed sample size in terms of the likelihood of achieving each aim.**

Over the course of the study period, there will be a finite number of possible enrolled subjects. We expect to enroll a total target sample size of  $N = 80$  eligible subjects. Our funding will provide for 40 patients to undergo the new treatment plan with 40 standard dressing subjects as a comparison. We anticipate that about 10 subjects will have incomplete data due to compliance, drop-out, and other causes. This will result in a recruitment of up to 90 subjects in order to result in 80 subjects completing the trial.

Our primary goal is to test the difference between two independent groups at a specific time point (namely, one week post op). We can think of this as a two independent groups t-test. With  $n_1=40$  vs  $n_2=40$ , we will have 80% power to reject the null if the difference between the means of the two conditions were 0.63 standard deviations apart (and with greater power if the differences were bigger). Any difference of less than 0.63 SDs would be seen as not clinically significant. Small differences in the score of 1-2 points would fall within this and can be attributed to observer differences and would likely not be sensitive for detecting any risk for surgical infection.

The experimental dressing is expected to have benefit by reducing wound healing characteristics related to complications (ASEPSIS score) and subsequently reducing postoperative infections. There is an extremely low rate of infections in primary total hip arthroplasty surgeries and infection cannot be measured with this limited population (0.5% to 3.0% of the population). Adverse secondary events also have a low incidence and our study is not designed or powered to identify a statistically significant difference in these events, although such events will be recorded and examined for exploratory purposes. The ASEPSIS score allows a lower sample size that is within our reach to detect changes and will be used to identify infection risk.

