## Part B. Direct Interaction

### B.1. Methods of recruiting

B.1.1. Check all the following means/methods of subject recruitment to be used:\*

- In person
- Participant pools
- Presentation to classes or other groups
- Letters
- Flyers
- Radio, TV recruitment ads
- Newspaper recruitment ads
- Website recruitment ads
- Telephone script
- Email or listserv announcements
- Follow up to initial contact (e.g., email, script, letter)
- Other

B.1.2. Describe how subjects will be identified

Patients will be patients previously scheduled for primary total hip arthroplasty in [name] clinic.

B.1.3. Describe how and where subjects will be recruited and address the likelihood that you will have access to the projected number of subjects identified in A.2.

All patients will be previously scheduled for primary total hip arthroplasty in [name] clinic. [name] performs approximately 10 primary total hip arthroplasties per month.

B.1.4. Describe how you will protect the privacy of potential subjects during recruitment

All patient data will remain on secured servers.

B.1.5. Describe how subjects will be contacted, if not addressed above

Subjects will be previously scheduled for clinic visits in preparation of total hip arthroplasty surgery.

B.1.6. Describe who will do the recruiting

Recruiting will be performed by the resident surgeon during clinic visits.

B.1.7. Describe efforts to ensure equal access to participation among women and minorities

All patients regardless of demographics will be recruited. No difference in recruiting efforts will be made.

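### The accrual stop rule in A.7.4 acts on a single slow month and ignores cumulative enrolment, so it can end a trial still on course for 90 patients in the year

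*Combined protocol and SAP*

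**What the plan says.** Section A.7.4 (criteria to stop the entire study) has two accrual rules.

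- **Companion rule, in words:** "If it does not appear that we will be able to establish our numbers in 1 year, the project will be halted". It has no rate, review date or method of projection.
- **Numeric rule:** after stating "We anticipate being able to sign up 2 patients a week", the section continues: "If we are averaging less than 1 patient a week for a month we will stop the study". The reason given is that catching up from such a shortfall would probably be hard. The rule sets no condition on cumulative enrolment, makes no start-up allowance, and does not say whether a month is a calendar month, a 4-week block or a rolling window.

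The figures that bear on these rules are elsewhere:

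- A.8.4, target: "This will result in a recruitment of up to 90 subjects in order to result in 80 subjects completing the trial".
- A.4.5, study period: "Stop: 1 year from start date or earlier depending on number enrolled".
- A.4.2, follow-up: "They will be monitored until their 6 week visit for any complications".
- B.1.3, caseload: the one surgeon whose clinic supplies the patients "performs approximately 10 primary total hip arthroplasties per month".

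**The concern.** The rule is meant to detect a trial that cannot recruit its numbers in the time available. That depends on enrolment to date and the weeks remaining, and the numeric rule uses neither. Read literally, it treats a 3-patient month the same way with 10 patients enrolled as with 75.

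Recruitment comes from a single clinic. Two a week already needs about 87% of its caseload before exclusions and refusals, so an isolated slow month is plausible. If the rule were then followed, the trial would end before its only confirmatory analysis, the one-week t-test in A.8.1, had its planned 80 completers. Patients would already have been randomized, and power would fall for a reason unrelated to feasibility.

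**Working it through.** **The plan's own figure.** A.8.4 states 80% power at 0.63 SD with 40 per arm. The documents give no alpha, so two-sided 0.05 is assumed. By the normal approximation, power = Φ(0.63 × √(40/2) − 1.96) = 80.4%; the noncentral t gives 79.5%. The figure reproduces, and 80 + 10 = 90 agrees with the recruitment target. The plan gives no operating characteristics for the accrual rule.

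**Slack at the planned rate**
- Time to 90: 90/2 = 45 weeks. Slack in the year: 52 − 45 = 7 weeks.
- If 6-week follow-up must also fit: 46 − 45 = 1 week.
- Cost of a 4-week month with 3 enrolments instead of 8: 5/2 = 2.5 weeks.

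**An illustrative case.** At 2 a week, 75 are enrolled at week 37.5. After a 3-patient month there are 78 at week 41.5, with 12 to go.
- Enrolling to week 52: 10.5 weeks remain, so 12/10.5 = 1.14 a week is enough.
- Leaving 1 week for the primary endpoint: 12/9.5 = 1.26 a week.
- Leaving 6 weeks for full follow-up: 12/4.5 = 2.67 a week, more than the caseload of 10 × 12/52 = 2.31. At 2 a week the trial would finish with 78 + 9 = 87. With 80/90 completing, that is 38.7 per arm and about 79% power.

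The rule stops the study in every case.

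**Chance of a trip.** An average below 1 a week means 3 or fewer in 4 weeks, or 4 or fewer in a 4.33-week calendar month. The documents give no accrual distribution, so a range is shown.

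| Assumption | Per period | Before 90, or over 12 months |
|---|---|---|
| Fixed 10 cases a month, 87% enrolling (2 a week), 4 or fewer per calendar month | 0.07% | 0.9% over 12 months |
| Fixed 10 cases a month, 75% enrolling (expected 90 a year), 4 or fewer per calendar month | 2.0% | 1 − (1 − 0.0197)^12 = 21% |
| Poisson, 2 a week, 4-week blocks | P(X ≤ 3 given mean 8) = 4.2% | 1 − (1 − 0.0424)^11 = 38% |
| Poisson, 2 a week, calendar months | P(X ≤ 4 given mean 8.67) = 6.7% | 1 − (1 − 0.0673)^10 = 50% |
| Poisson, 2 a week, rolling 4-week window | n/a | about 66% (simulation) |

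Of the simulated 2-a-week trials that would have reached 90 within 52 weeks, 35% trip the rule in non-overlapping 4-week blocks.

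**Is the trigger tied to the target?** The steady rate needed is 90/52 = 1.73 a week, or 90/46 = 1.96 if follow-up must fit. The trigger is 1 a week. Perfectly steady rates of 1.0, 1.25 and 1.5 a week give 52, 65 and 78 in a year. None of these would trip the numeric rule, so only the companion rule addresses them.

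**The case against.** **The plan already deals with slow accrual.** A reader might infer that A.7.4 lets an infeasible trial run the whole year, because steady rates of 1.0 to 1.73 a week stay at or above the numeric trigger. The documents do not support that. The companion rule in the same section halts the project if the numbers look unreachable in 1 year, which is exactly this case. What stands is narrower: the rule with a number is not tied to the target, and the rule tied to the target has no date or method. In addition, a true rate of 1.5 a week with Poisson variation would trip the numeric rule at some point in about 88% of trials.

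**High trip probabilities at lower rates are not false stops.** At 1.5 a week, or with 60–70% of 10 cases a month enrolling (72–84 a year), the expected total is short of 90. With a fixed caseload of 120 a year, the chance of reaching 90 is 0.04% at 60% enrolment and 14% at 70%. Stopping those trials is mostly what the plan intends, so they are left out of the range.

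**The plan's reason can be defended.** If all follow-up must fit in the year, the slack is 1 week and one 3-patient month uses more than that. This stands as a reading. It does not justify an automatic stop, since the illustrative trial would then miss 90 by 3 patients and lose about 1 point of power.

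**Arrivals may be regular.** Patients are already scheduled for elective surgery, so Poisson variation may be too wide. This stands, and it is why the range starts below 1%.

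**Conclusion.** As written, one month averaging below 1 patient a week ends the study whatever has been enrolled, and this can stop a trial on course for 90 in the year. That follows from the text and the plan's own rates. How likely it is does not: under 1% with a regular caseload and 87% enrolling, about 21% at 75% enrolling, about 38% with Poisson arrivals in 4-week blocks, and about 66% on a rolling window. The documents do not favour any value in that range. The 75% case is borderline, since its expected yearly enrolment is exactly 90.

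The loss depends on when the stop falls. As an illustration, 20 completers per arm would leave about 50% power at 0.63 SD (two-sided 0.05 assumed).

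This is a minor weakness in an operational rule. A reader might infer that it compromises the primary comparison, but the trigger does not use outcome data and so does not bias the t-test.

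**What to change.** Replace the automatic stop in A.7.4 with one sentence: a month averaging below 1 patient a week triggers a projection of final enrolment from cumulative accrual, and the study is halted only if that projection cannot reach the target within the year. This puts a method behind the companion rule that the plan already states. The sentence should also define a month and say whether the year must contain the 6-week follow-up, because the answer can turn on it. In the illustrative case 78/41.5 = 1.88 a week, which projects to 97.7 at 52 weeks but 86.5 at 46.

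No extension of the enrolment window is proposed. A.4.5 fixes the period at 1 year, and A.8.4 bases the sample size partly on the time available. The safety stopping criteria stay as they are.

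The cost is one sentence and an IRB amendment. The downside is that a truly failing trial may run a month or two longer. In the first month the projection rests on that month alone, so the new rule gives no protection there unless the first review is set later.
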